In both groups, intraoperative maintenance rate of crystalloid fluids is 3 ml·kg⁻¹·hr⁻¹ ideal body weight. ProAQT®-derived hemodynamic data and peripheral perfusion index and SpO₂ will be acquired at the following time points: 5 min after induction of anesthesia, 5 min after start of pneumoperitoneum and head-up tilting, 5 min after end of pneumoperitoneum, cessation of volatile anesthetics, and 5 min after extubation. Subjects of the GDHT group will be managed according to the ERAS algorithm utilizing ProAQT® parameters to maintain the cardiac index ≥ 2.5 l·min⁻¹·m⁻².⁶¹ In brief, if cardiac index < 2.5 l·min⁻¹·m⁻², a bolus of 150 ml of crystalloid fluid will be given until the stroke volume variation is < 10%. If cardiac index < 2.5 l·min⁻¹·m⁻² despite the stroke volume variation of ≥ 10% following fluid challenge, continuous intravenous infusion of dopamine 5–10 µg·kg⁻¹·min⁻¹ will be administered. If mean arterial pressure is < 70 mmHg despite cardiac index ≥ 2.5 l·min⁻¹·m⁻², intravenous infusion of norepinephrine 2–10 µg·min⁻¹ will be used. (Figure 3)

Subjects allocated to the control group are hemodynamically managed as per anesthesiologist preference. Typically, isolated hypotension (20% decrease in mean arterial pressure below baseline or < 60 mmHg) is treated by single or consecutive boluses of norepinephrine 5 or 10 µg. If hypotension persists, repeat boluses of ephedrine 4 mg will be administered until mean arterial pressure is above 60 mmHg. If hypotension is accompanied by signs of hypovolemia (urine output < 0.5 ml·kg⁻¹·hr⁻¹ and/or an increase in heart rate > 20% above baseline), crystalloid or colloid fluids will be given until urine output and/or heart rate are normalized. If hypotension persists despite volume challenge, norepinephrine will be used.

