In both groups, the fluid, inotrope, and vasopressor responsiveness, ProAQT® parameters (cardiac index, stroke volume variation, systemic vascular resistance, and mean arterial pressure), and the signals of pulse oximetry (perfusion index and SpO₂) will be evaluated and recorded for each 15-min interval throughout the surgery. In control group, the ProAQT® monitoring will be concealed from the anesthetist in charge. Artifact-free signals are considered valid for statistical analysis. At the end of surgery, all participants will receive a manual recruitment maneuver of 30 to 40 cmH₂O for 10 s three times. In all patients, cessation of volatile anesthetics will be timed to facilitate early awakening after wound closure. All patients

will be decurarized from rocuronium-induced neuromuscular blockade with sugammadex dosed at $2 \text{ mg} \cdot \text{kg}^{-1}$ ideal body weight + 40%.⁶²

[figure not shown]

Figure 3: Goal-directed hemodynamic algorithm to guide intraoperative fluid therapy and the use of inotrope and vasopressor

Primary outcome is a composite of major complications according to the European Perioperative Clinical Outcome definitions within 30 days after surgery, including myocardial ischemia or infarction, arrhythmia, acute kidney injury, gastrointestinal bleeding, anastomotic breakdown, surgical site infection, and hospital-acquired pneumonia.⁶³ Secondary outcomes comprise longitudinal changes of ProAQT® parameters (cardiac index, stroke volume variation, systemic vascular resistance, and mean arterial pressure) and signals of pulse oximetry (peripheral perfusion index and SpO₂), relative change of arterial partial pressure of oxygen (PaO₂)/FiO₂, PaO₂/FiO₂, serum glucose, base excess values after induction of anesthesia and at the end of surgery, clinically relevant hypotensive episodes (decrease in mean arterial pressure > 20% for more than 15 min requiring vasopressors), need for intensive care, time to ambulation, time to first oral intake, and length of hospital stay. Episodes of major complications will be evaluated by research staff blinded to group assignment.

Sample Size Estimation

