According to prior study⁶⁴, at least 80 patients in each group of GDHT and control are needed to detect a significant difference, accepting a type I error of 5% and type II error of 10% with anticipated incidence of postoperative major complications 30% in GDHT group and 55% in control group in Substudy 4.⁶⁵ To allocate 60 subjects to each group of video intubating stylet, video laryngoscopy, and direct laryngoscopy in Substudy 3, a total of 180 subjects are needed for the factorial trial. There are about 120 obese people undergoing LSG at our hospital per year. Considering the patient selection criteria and possible patient refusal, an estimated sample of 90 patients will be recruited per year in this trial. Therefore, it will take about 2 years for patient recruitment.

Statistical Analysis

Baseline patient characteristics and outcome variables will be compared between two groups using chi-square tests or Fisher's exact tests for categorical variables and either t tests or Wilcoxon rank sum tests for continuous variables, as appropriate. For three and four group comparisons, chi-square tests or Fisher's exact tests will be used for categorical variables and either one-way ANOVA or Kruskal-Wallis rank test for continuous variables, as appropriate. *Post hoc* pairwise comparisons will be performed using the Bonferroni correction. For longitudinal data, generalized linear mixed models or generalized estimating equations models will be used to analyze the association between exposure variables and outcomes of interest. For time to event data, Kaplan-Meier method and log-rank test will be applied for group comparisons. Multivariable logistic regression, simple linear regression, or Cox proportional hazards regression analyses will be used to identify potential influential factors of outcomes. A two-sided significance level of 0.05 will be used to define statistically significant difference. All the statistical analyses will be conducted using Statistics Analysis System (SAS), Version 9.4 (SAS Institute Inc., Cary, NC, USA).

References

1. World Health Organization. Fact sheets: Obesity and overweight. <https://www.who.int/en/news-room/fact-sheets/detail/obesity-and-overweight> (accessed on December 5, 2020).
2. Blüher M. Obesity: global epidemiology and pathogenesis. *Nat Rev Endocrinol.* 2019;15:288-98.

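### Substudy 4: the written dopamine trigger overlaps the fluid rule and leaves a low cardiac index with stroke volume variation below 10% without any step; the inequality is probably reversed

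*Combined protocol and SAP*

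**What the plan says.** The Substudy 4 section of the combined protocol and SAP states that GDHT patients are "managed according to the ERAS algorithm utilizing ProAQT® parameters to maintain the cardiac index ≥ 2.5" l/min/m². Three rules follow, in this order:

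1. **Fluid.** When CI is below 2.5, "a bolus of 150 ml of crystalloid fluid will be given until the stroke volume variation is < 10" (percent). No maximum number of boluses or total volume is given.
2. **Dopamine.** When CI is below 2.5 "despite the stroke volume variation of ≥ 10% following fluid challenge, continuous intravenous infusion of dopamine" is given at 5–10 µg/kg/min.
3. **Norepinephrine.** "If mean arterial pressure is < 70 mmHg despite cardiac index ≥ 2.5", norepinephrine is infused at 2–10 µg/min.

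The text presents these rules as a short summary of a cited algorithm and refers to Figure 3, captioned "Goal-directed hemodynamic algorithm to guide intraoperative fluid therapy and the use of inotrope and vasopressor". The figure was not available for this review.

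**The concern.** Rule 1 treats SVV below 10% as the point at which fluid is complete. An inotrope would be expected next if CI were still low at that point. Rule 2 instead ties dopamine to SVV of 10% or more, the range in which rule 1 still calls for fluid.

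These rules are the Substudy 4 intervention. Followed literally, they start dopamine while the fluid rule is still active and give no trigger for it once the fluid target has been met and CI remains low. Anesthesiologists could resolve this in different ways, so the treatment delivered would be neither uniform nor reproducible from the text. The timing of fluid and dopamine also bears on what is measured: CI, SVV and mean arterial pressure (MAP) are secondary outcomes, and the primary composite includes arrhythmia, myocardial ischemia and acute kidney injury.

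**Working it through.** **Inputs.** All thresholds come from the GDHT paragraph of Substudy 4: CI 2.5 l/min/m², SVV 10%, MAP 70 mmHg. I take the fluid rule to apply only while CI is below 2.5, as its opening condition says.

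**After at least one fluid challenge.** Two levels each of CI, SVV and MAP give 2 × 2 × 2 = 8 states. No rule uses MAP when CI is below 2.5, and none uses SVV when CI is at least 2.5, so the states pair up:

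| CI | SVV | MAP | States | As written | Dopamine condition changed to SVV < 10% |
|---|---|---|---|---|---|
| < 2.5 | ≥ 10% | either | 2 | fluid and dopamine | fluid |
| < 2.5 | < 10% | either | 2 | no rule | dopamine |
| ≥ 2.5 | either | < 70 | 2 | norepinephrine | norepinephrine |
| ≥ 2.5 | either | ≥ 70 | 2 | at goal | at goal |

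As written, 4 of 8 states are clear, 2 carry two instructions and 2 carry none. With the inequality reversed, all 8 have one disposition. The gap includes patients with CI below 2.5, SVV below 10% and MAP below 70, because rule 3 requires CI of at least 2.5. It is the state reached whenever fluid achieves its own endpoint without restoring CI.

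**Before any bolus.** Low CI with SVV of 10% or more clearly calls for fluid. Low CI with SVV already below 10% is unsettled: the stopping point for fluid is already met, and dopamine is worded as following a challenge. A literal reading might allow one bolus, since CI alone opens rule 1, but no step follows it. Reversing the inequality does not by itself settle this case.

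**Wording.** In rule 3, *despite* introduces a target that has been met (CI of at least 2.5). Read the same way, rule 2 should refer to the fluid target having been met, which is SVV below 10%. This supports a reversed sign rather than an intended rule.

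**Patients affected.** Only GDHT patients still below CI 2.5 after fluid are affected, and the documents do not give that share. Sample Size Estimation says "a total of 180 subjects are needed for the factorial trial". Assuming equal allocation, 180 / 2 = 90 are in the GDHT arm. Assumed shares of 5%, 10%, 25% and 50% give 90 × 0.05 = 4.5, 90 × 0.10 = 9, 90 × 0.25 = 22.5 and 90 × 0.50 = 45 patients.

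**Sample size.** The planned figure of at least 80 per group is not in dispute. With 30% versus 55%, two-sided 5% and 90% power, n = [1.960 √(2 × 0.425 × 0.575) + 1.282 √(0.30 × 0.70 + 0.55 × 0.45)]² / 0.25² ≈ 80.1, or 81 after rounding up; power at 80 per group is 90.0%. None of these inputs involves the dopamine rule.

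**The case against.** The strongest objection is that the governing algorithm has not been seen. The text is a summary, and both Figure 3 and the cited source may carry the right branch. In that case this is a one-character error that need not have changed treatment. This limits what can be said about clinical consequence. It does not rescue the sentence: if the figure is right, text and figure contradict each other; if the figure repeats the text, the algorithm itself is wrong.

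A second objection is that fluid and dopamine are not mutually exclusive. The sentence could mean that an inotrope is added when a challenge has corrected neither CI nor SVV. That reading softens the overlap to a missing bolus limit. It leaves low CI with SVV below 10% without a step, which is the more serious half.

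Three smaller points stand. The state count doubles one overlap and one gap, because MAP plays no part when CI is low. The patient range rests on an assumed share that nothing in the documents anchors. And the control-arm instruction "If hypotension persists despite volume challenge, norepinephrine will be used" is a weak comparator: it describes usual practice under anesthesiologist preference and treats hypotension, not low CI. It shows the expected order of volume first and drug second, and no more than that.

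**Conclusion.** The concern holds for the written text of the GDHT algorithm. Once a challenge has been given, low CI with SVV of 10% or more falls under two rules, and low CI with SVV below 10% falls under none; no other visible text fills the gap. A reversed inequality is the likely cause, though the text alone cannot prove it.

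In logic, the size is one overlap and one gap, or 4 of the 8 post-challenge states. In patients, it is about 5 to 45 of an assumed 90, which is illustrative only. An effect on the treatment contrast is possible but cannot be quantified from the documents. No stated sample size or power changes. Because this is a treatment threshold in the intervention under test, it should be corrected.

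**What to change.** Change the dopamine condition to: CI below 2.5 despite SVV below 10% following fluid challenge. If dopamine at persistent SVV of 10% or more is really intended, state a maximum number of 150 ml boluses and add an action for CI below 2.5 with SVV below 10%. In either case, say what is done when CI is below 2.5 and SVV is already below 10% before any bolus. The clinical team should confirm the rule and make the text and Figure 3 agree before the algorithm is used.

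The cost is a short protocol correction, a check against the figure and a staff notice. Sample size, randomization and data collection do not change.

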After preoxygenation using facemask with pure oxygen $10\text{ l}\cdot\text{min}^{-1}$ until end-tidal fractional oxygen concentration in the expired air (EtO_2) $\geq 80\%$, general anesthesia will be induced with propofol $1.5\text{--}2.0\text{ mg}\cdot\text{kg}^{-1}$ ideal body weight and fentanyl $1\text{--}2\text{ }\mu\text{g}\cdot\text{kg}^{-1}$ total body weight. Tracheal intubation will be facilitated with rocuronium $0.8\text{--}1.0\text{ mg}\cdot\text{kg}^{-1}$ ideal body weight. After induction, a radial artery catheterization will be performed for continuous monitoring of arterial pressure and measurement of serum glucose. In the designated patients, 8 mg of dexamethasone or placebo will be given intravenously within 10 minutes after the induction of anesthesia. Anesthesia will be maintained with 2–3 vol% sevoflurane and 60% oxygen in nitrogen, whereas the fraction of inspired oxygen (FiO_2) 0.8–1.0 will be used during pneumoperitoneum to ensure oxygen saturation higher than 92%. If the value of surgical pleth index (CARESCAPE B650 Monitor, GE Healthcare, Chicago, IL, USA) is more than 50 or heart rate or blood pressure increases by more than 20% from baseline values during surgery, an intravenous bolus of fentanyl 25 or 50 μg will be given. Besides, the concentration of sevoflurane can be adjusted as clinically appropriate.

After surgery, all patients will receive supplemental oxygen, and pain will be relieved with ketorolac 15 to 30 mg. The need for postoperative opioids will be at the discretion of the anesthesiologist, and the dose will be adjusted according to clinical needs. Patients who request rescue antiemetic therapy or who have an emetic episode will be given droperidol 1.25 mg. If symptoms persist, metoclopramide 10 mg will be administered.

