Primary outcome is the best glottis visualization, graded according to Cormack and Lehane's classification with external laryngeal pressure applied.⁵⁷ Glottic views graded as III or IV are regarded as difficult. Secondary outcomes are number of intubation attempts, the percentage of glottic opening (POGO) score, time to intubation, lowest SpO_2 during intubation, and ease of intubation. Each video stylet or laryngoscope blade insertion is defined as an intubation attempt. Minor adjustments of patient's position or tube stylet are not considered separate attempts. The POGO score is defined by the best glottis visualization (0%, 25%, 50%, 75%, or 100%).⁵⁸ Time to intubation is defined as the interval between intubating stylet or laryngoscope insertion into oral cavity and EtCO_2 detected. Ease of intubation is a subjective assessment of anesthesiologists, rated as (1) very easy, (2) easy, (3) moderate, (4) difficult, and (5) impossible.⁵⁹ Safety outcomes are upper airway injury (bleeding, abrasion or laceration), dental injury (bleeding, trauma, fracture), respiratory complications (laryngospasm, bronchospasm, aspiration), cough (mild, moderate, severe), sore throat (mild, moderate, severe), and hoarseness (noticed by the patient only, apparent to an observer). Research staff blinded to group allocation will evaluate the complications at the 2nd and 24th postoperative hours.

Substudy 4: An investigation of the putative benefits of goal-directed hemodynamic therapy targeting cardiac index in obese patients undergoing laparoscopic sleeve gastrectomy: an open-label randomized controlled trial

At the operation room, we will apply the Masimo Radical 7 pulse oximetry (Masimo Corp., Irvine, CA, USA) to the fingers of all enrolled patients to measure perfusion index and SpO₂ throughout the surgery. After the placement of a tracheal tube, patients will receive ventilator support with the tidal volume 6–8 ml·kg⁻¹ ideal body weight, a respiratory rate of 10–15 min⁻¹ and PEEP 5 cmH₂O applied by the ventilator.⁶⁰ The FiO₂ will be set at 0.3–0.7 to maintain SpO₂ ≥ 98% throughout the surgery. Each patient will be randomly allocated to one of each of the following two groups: goal-directed hemodynamic therapy and control.

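### In Substudy 4, intraoperative SpO₂ is largely uninformative because FiO₂ is titrated to hold it at target, and PaO₂/FiO₂ has no baseline-adjusted analysis

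*Combined protocol and SAP*

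**What the plan says.** All references are to the combined protocol and SAP.

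- **Oxygen rule, Substudy 4 (all patients):** "The FiO₂ will be set at 0.3–0.7 to maintain SpO₂ ≥ 98% throughout the surgery".
- **Oxygen rule, Substudy 1 (the same factorial patients):** an FiO₂ of "0.8–1.0 will be used during pneumoperitoneum to ensure oxygen saturation higher than 92" per cent.
- **SpO₂ as an outcome:** the Substudy 4 secondary outcomes include longitudinal change in "signals of pulse oximetry (peripheral perfusion index and SpO₂"). These signals are recorded at 15-minute intervals during surgery and at named time points, the last being 5 min after extubation. FiO₂ is not among the items listed for recording alongside them.
- **PaO₂/FiO₂ as an outcome:** it appears in two forms, "relative change of arterial partial pressure of oxygen (PaO₂)/FiO₂" and then the ratio itself ("relative change of arterial partial pressure of oxygen (PaO₂)/FiO₂, PaO₂/FiO₂, serum glucose"), in a list that ends "base excess values after induction of anesthesia and at the end of surgery".
- **Recruitment:** "At the end of surgery, all participants will receive a manual recruitment maneuver of 30 to 40 cmH₂O for 10 s three times". Its order relative to the final blood gas is not stated.
- **Analysis:** the Statistical Analysis section names t or Wilcoxon tests for two-group continuous variables, and mixed models or GEE for longitudinal data. It does not specify a baseline-adjusted comparison for PaO₂/FiO₂.

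**The concern.** Intraoperative SpO₂ is both an outcome and the variable that FiO₂ is adjusted to control. If one arm exchanges gas less well, the anesthetist raises FiO₂ and saturation returns to target. The difference moves into FiO₂, and no model fitted to SpO₂ alone can recover it. Goal-directed fluid could help or harm oxygenation, so a flat SpO₂ comparison could be misread as evidence of no effect.

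PaO₂/FiO₂ takes the oxygen fraction into account, at least in part, so it is the more useful measure. Here the question is efficiency. Relative change puts a noisy baseline in the denominator, and a test of the end value ignores the baseline. Both leave unused information that the trial already collects. With two forms listed and neither given priority, the choice of analysis also stays open.

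The final blood gas and the recruitment maneuver share one time label. The maneuver is meant to change oxygenation, so a mixture of orders adds avoidable variation. Because Substudy 4 is open-label, the order could also drift by arm.

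**Working it through.** **The plan's own figure.** The only sample size stated for Substudy 4 is 80 per group for the primary composite (30% v 55%, two-sided 5%, power 90%). With pooled variance under the null, n = [1.96·√(2·0.425·0.575) + 1.282·√(0.30·0.70 + 0.55·0.45)]² / 0.25² = (1.370 + 0.867)² / 0.0625 ≈ 80.1, or 81 when rounded up. The stated 80 reproduces. No effect size, SD or power is given for any oxygenation outcome, so every input below is an assumption except the group size. That is 180/2 = 90 per arm, if the arms are equal; Substudy 4 does not state its ratio.

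**SpO₂ under titration (simulation).** Untitrated SpO₂ was given a mean of 97–98.5 and an SD of 1.5–2, with a true arm difference of 1.0–1.5 points. Each reading below 98% was returned to 98–99%, as the Substudy 4 rule intends. The remaining difference is about 0.07–0.35 points, a loss of roughly 70–95%. This assumes titration always succeeds. Where FiO₂ is already at the 0.7 limit, some difference would still show.

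**PaO₂/FiO₂.** Assumptions: mean 350, SD 90, true end-of-surgery difference 35 (35/350 = 10%), 90 per arm.

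- End value: SE = 90·√(2/90) = 13.42, and 35/13.42 = 2.61. Power ≈ Φ(2.61 − 1.96) = 74%.
- ANCOVA: SE = 13.42·√(1 − ρ²), which is 12.80, 11.62 and 9.58 at ρ = 0.3, 0.5 and 0.7. Power ≈ 78%, 85% and 95%.
- Relative change, (end − baseline)/baseline, is skewed by small denominators and was simulated.

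Simulated power, with all three analyses on the same data:

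| Baseline correlation | Relative change | End value | ANCOVA |
|---|---|---|---|
| 0.3 | 44% | 72–73% | 76% |
| 0.5 | 60% | 72–73% | 84% |
| 0.7 | 83% | 72–73% | 95% |

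Repeat runs move these by a few points at most. The arm difference in relative change is about 0.107 against a true 0.10, so the effect is kept.

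A log-normal model (baseline 300, effect +10%) points the same way. At log-SD 0.3 and correlation 0.3, 0.5 and 0.7, power for relative change is 0.42, 0.55 and 0.78. For the end value it is 0.55, 0.55 and 0.53, and for ANCOVA 0.58, 0.66 and 0.82. At correlation 0.9, relative change and ANCOVA are equal to rounding.

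**Recruitment.** The documents give no basis for the size of any attenuation. As a scale only, take an effect of 0.5 SD with a fraction k lost. Power = Φ(0.5(1 − k)/√(2/90) − 1.96), which is 0.92, 0.71, 0.39 and 0.13 for k = 0, 0.25, 0.5 and 0.75.

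**The case against.** A reader might infer that the Substudy 4 oxygenation outcomes as a whole lose most of any arm difference and would show nothing whichever way the therapy acts. The documents do not support that, for four reasons.

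- **PaO₂/FiO₂ keeps the effect.** Relative change shows about the true 10%. The raw ratio is listed as well, and its end-value test already has about 72–73% power under the same assumptions. At correlation 0.3 the gain from ANCOVA over that test is only about 4 points. The large gap, 44% v 76%, is against the weaker of the two planned forms.
- **The SpO₂ argument does not carry over to PaO₂/FiO₂,** because dividing by FiO₂ accounts at least in part for titration. The SpO₂ reading after extubation also lies outside the intraoperative rule.
- **The recruitment point is an unstated order.** If blood is drawn first, it disappears. The maneuver is the same in both arms, so by itself it creates no bias between them.
- **The titration model is unsettled** while Substudy 1 gives a different oxygen rule. Where FiO₂ is set by surgical phase, the FiO₂ required would also say little.

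All four stand, and they confine the point to intraoperative SpO₂ and to analysis efficiency. One could add that the mixed models named for longitudinal data might be applied to the two PaO₂/FiO₂ values. The plan does not say so, and a relative change is a single value per patient.

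**Conclusion.** The point holds in limited form.

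- **Intraoperative SpO₂** is largely uninformative as an arm comparison under the Substudy 4 rule. The direction follows from the text. The size, about 70–95% of a 1.0–1.5 point difference lost, rests on assumed saturations and on titration that succeeds.
- **PaO₂/FiO₂** retains any arm difference in either listed form but is analysed less efficiently than it could be. Under the stated assumptions ANCOVA gains about 12–32 points of power over relative change (95 − 83 and 76 − 44) and about 3–23 over the end value (76 − 73 and 95 − 72). This takes the post-induction sample as drawn before the arms' management diverges.
- **Blood-gas order** needs a minor clarification. No loss can be derived from the documents.
- **The oxygen rules** in Substudies 1 and 4 contradict each other for the same patients.

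These are secondary outcomes. The primary composite and its sample size are unaffected.

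**What to change.** 1. Record FiO₂ with every SpO₂ reading, and interpret SpO₂ only together with it, for example as SpO₂/FiO₂. Report the post-extubation reading separately.
2. Name one main PaO₂/FiO₂ analysis: ANCOVA of the end-of-surgery value on the post-induction value, in place of relative change.
3. State one fixed point, relative to the recruitment maneuver, at which the end-of-surgery blood gas is drawn in every patient. This is a sampling rule and leaves the maneuver unchanged.
4. Reconcile the FiO₂ and saturation rules in Substudies 1 and 4. Which rule applies is for the investigators to decide. The analysis should then state in which phases FiO₂ was titrated and in which it was set by phase.

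The cost is one recorded field, one sequencing line and some analysis wording, with no extra patients. Items 1 and 3 should be settled before data are collected, since FiO₂ that was not recorded and an order that was not fixed may be unrecoverable later. Item 2 uses a value the trial already collects and should be fixed before arm comparisons are seen.

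### Substudy 4 counts a hypotensive episode only if it required vasopressors, but the written vasopressor triggers differ by arm, so the same pressure fall can be counted differently

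*Combined protocol and SAP*

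**What the plan says.** The outcome is in the secondary outcome list of Substudy 4: "clinically relevant hypotensive episodes (decrease in mean arterial pressure > 20% for more than 15 min requiring vasopressors". An episode must therefore meet a depth, a duration and a treatment condition. The section does not say which reading is the baseline, which data the episode is derived from, which drugs count, or whether requiring a vasopressor means that one was given or that someone judged it necessary.

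The same section describes haemodynamic management by arm.

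- **Control.** "Subjects allocated to the control group are hemodynamically managed as per anesthesiologist preference". The usual pattern is: "Typically, isolated hypotension (20% decrease in mean arterial pressure below baseline or < 60 mmHg) is treated by single or consecutive boluses" of norepinephrine. If hypotension persists, ephedrine boluses follow until MAP is above 60 mmHg. With signs of hypovolaemia, fluids come first: "If hypotension persists despite volume challenge, norepinephrine will be used".
- **GDHT.** The algorithm is a summary, opening "In brief, if cardiac index". Below a cardiac index of 2.5 the response is fluid boluses and then "continuous intravenous infusion of dopamine". The norepinephrine rule begins "If mean arterial pressure is < 70 mmHg despite cardiac index" and applies when the index is at least 2.5. No trigger relative to baseline is printed. Figure 3, which holds the algorithm, is not visible in the text available.

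Substudy 4 is open-label. Blinded evaluation is stated for major complications only.

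**The concern.** The treatment condition makes the count depend partly on the rule each arm follows. The usual control trigger almost coincides with the outcome's own 20% criterion. The printed GDHT trigger is an absolute pressure combined with a cardiac index condition. Two patients with the same pressure trace can then be classified differently because of their allocation.

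What is at stake is the reading of this one outcome. A difference between arms, or the absence of one, could not be taken as a statement about hypotension alone, because it would mix how often pressure fell with how often the arm's rule called for a vasopressor.

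**Working it through.** The plan gives no figure for this outcome. Its one sample size, 80 per group, belongs to the primary composite and plays no part here.

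**Step 1: where the printed triggers disagree.** The outcome needs MAP below 0.8 × baseline. The GDHT norepinephrine trigger needs MAP below 70 mmHg (with cardiac index ≥ 2.5). They coincide at baseline = 70/0.8 = 87.5 mmHg. Above that there is a band from 70 mmHg up to 0.8 × baseline, of width max(0, 0.8 × baseline − 70):

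- baseline 85: 68 − 70 < 0, no band
- baseline 90: 72 − 70 = 2 mmHg
- baseline 95: 76 − 70 = 6 mmHg
- baseline 100: 80 − 70 = 10 mmHg

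Example: baseline 100, MAP 75 for 20 min, cardiac index at target. The fall is 25%, so the usual control trigger is met. MAP is not below 70, so the printed GDHT norepinephrine trigger is not. At a baseline of 87.5 or lower, every fall of more than 20% is below 70 and this gap closes.

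**Step 2: the low-cardiac-index branch.** The recording paragraph and the Figure 3 caption name inotrope separately from vasopressor. If dopamine is classed as the inotrope, a GDHT episode longer than 15 min that resolves on fluid or dopamine alone is not counted, whatever the baseline. If dopamine counts as a vasopressor, the episodes treated with it are counted. The plan does not say which.

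**Step 3: illustration of the Step 1 mechanism only.** No MAP distribution is given, so every input is an assumption: normal baseline MAP with SD 10 or 12; MAP during the fall a normal fraction of baseline with mean 0.75 or 0.80 and SD 0.08; identical falls in both arms; cardiac index ≥ 2.5; every episode below 70 mmHg treated in both arms. Let

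- g = P(fraction < 0.8 and MAP < 70)
- b = P(fraction < 0.8 and MAP ≥ 70)
- t = share of in-band control episodes treated
- k = chance that an in-band control fall lasts over 15 min, relative to a deeper one

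The GDHT/control ratio of counted episodes is g/(g + t × k × b). For mean baseline 100, SD 10, mean fraction 0.80, simulation gives g = 0.170 and b = 0.330; with t = k = 1 the ratio is 0.170/0.500 = 0.34. With k = 1 (2,000,000 draws per setting; ranges over the SD and fraction choices):

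| Mean baseline (mmHg) | t = 1 | t = 0.5 |
|---|---|---|
| 75 | 0.94–0.97 | 0.97–0.99 |
| 80 | 0.87–0.93 | 0.93–0.97 |
| 85 | 0.78–0.86 | 0.87–0.92 |
| 90 | 0.65–0.74 | 0.79–0.85 |
| 95 | 0.50–0.59 | 0.67–0.75 |
| 100 | 0.34–0.45 | 0.51–0.62 |

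The low baselines belong in the range. Substudy 1 places the arterial line after induction, and the first listed ProAQT reading is 5 min after induction, so a post-induction baseline is open under the plan.

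**Step 4: sensitivity to persistence.** At t = 1, k = 0.5 moves the ratio to 0.79–0.85 (mean baseline 90) and 0.51–0.62 (100). With k = 0.2 it is 0.90–0.93 and 0.72–0.80.

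**The case against.** A reader might infer that the outcome is biased in favour of GDHT, perhaps severely. The documents do not support that.

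- **Other routes act the opposite way.** Control treatment is discretionary, so some sustained control falls may go untreated and uncounted. Fluids-first treatment that restores pressure only after 15 min also leaves a control episode uncounted. Neither can be sized.
- **In-band control falls may not last.** They are typically treated from the 20% threshold, so many could end within 15 min. That would be a real difference in hypotension, and it shrinks the artefact (Step 4). The example in Step 1 presumes that the control episode outlasts 15 min.
- **Control treatment within the band is uncertain.** The ephedrine step aims only at MAP above 60 mmHg, already met at 75. Nothing in the documents supports a particular value of t.
- **The GDHT rule is a summary.** A relative-pressure criterion in Figure 3 would remove the band.
- **Two terms are open.** Excluding dopamine is a natural reading but not a stated rule, and requiring a vasopressor could mean judged need.
- **Much can be recovered from planned data.** Longitudinal MAP is already a secondary outcome, and MAP and vasopressor response are recorded for each 15-min interval in both arms.

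All of this stands as a limit on size and direction. None of it removes the dependence on treatment: discretion and an undefined treatment condition tie the count more closely to behaviour in an open-label arm. Longitudinal MAP limits the consequence but does not repair this outcome.

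**Conclusion.** The point holds, and it is minor. On the printed triggers, with baseline MAP above 87.5 mmHg, a fall lasting over 15 min with MAP between 70 mmHg and 80% of baseline can count in control and not in GDHT. If dopamine is classed as an inotrope, GDHT episodes that resolve on fluid or dopamine alone also go uncounted.

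Size and net direction are not established. For the trigger mechanism alone, the illustrative ratio runs from almost no effect to a large one, depending mainly on the baseline reading, which the plan leaves open. These ratios are not a forecast of net bias. They also assume that shallow and deep falls are equally likely to last over 15 min, and they move towards 1 if treated shallow falls end sooner.

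It would be wrong to extend this to the trial's main result. This is one secondary outcome on which no sample size was based.

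**What to change.** Define the episode as MAP more than 20% below baseline for more than 15 min, whether or not a vasopressor was given, and derive it identically in both arms. Name one baseline reading, the same for both arms. Use the stored arterial-pressure trend if it can be exported; otherwise use the 15-min log with a stated rule for consecutive low readings. Report vasopressor use as a separate outcome and list the qualifying drugs, stating whether dopamine is among them. The plan's present treated-episode count may be kept as a descriptive result. No treatment threshold is changed or endorsed.

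The cost is a few lines in the outcome definition, plus confirming that the trend is stored: the documents describe continuous arterial monitoring but recording only by 15-min interval and at set time points ("ProAQT®-derived hemodynamic data and peripheral perfusion index and SpO₂ will be acquired at the following time points").

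There are two downsides. The main count loses its treatment-based marker of clinical relevance. The log is also coarse. Assuming one spot reading every 15 min at random phase, an episode of D min (15 < D < 30) yields two low readings with probability (D − 15)/15: 5/15 = 33% at 20 min, so about two thirds are missed, and 10/15 = 67% at 25 min. Episodes of 30 min or more are all caught. A single-reading rule would instead also count 5/15 = 33% of 5-min dips and 10/15 = 67% of 10-min dips. For a given episode length the loss is the same in both arms.
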